## Subject Population(s) (Individuals/Records/Biospecimens)

Check all subject populations/data sources that apply to the research:

Adults Competent to Provide Informed Consent

## Maximum and Expected Number of Persons/Records/Biospecimens to be Enrolled

1. Click "Add Line" button above Enrollment Table to add a Category/Group
  - a. To change visibility of columns, click "Columns" button above Enrollment Table and select which Column rows to view.

2. Specify the maximum and expected numbers of individual-level information and/or biospecimens to be accessed/analyzed within each Category/Group

Category/Group
Adults
Age Range
18 and over
Maximum Number of Subjects, Subjects to be Consented or Reviewed/Collected
115
Number Expected to Complete the Study or Needed to Address the Research Question
105

Will this study only take place at UCI and does not involve other sites?

Yes

**Eligibility Factors (Inclusion/Exclusion Criteria)**

1. Click "Add Line" button above Eligibility Factors Table to add a inclusion/exclusion criteria
  - a. To change visibility of columns, click "Columns" button above Eligibility Factors Chart and select which Column rows to view.
2. Identify the factors for limited eligibility and provide a scientific rationale. Include additional rows for factors, as needed.

Category/Group Eligibility
Adult subjects over 18 years old undergoing posterior spinal fusion surgery will be recruited to participate in this study. There is no upper age limit for inclusion.
Inclusion Criteria
1. Subjects who provide written informed consent 2. Age 18 years old or

1. Subjects who provide written informed consent. 2. Age 18 years old or older (no upper age limit for inclusion) 3. Gender: male or female. 4. Surgery: Posterior spinal fusions

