Opioids are known to produce excellent intraoperative and postoperative pain relief. However, their effects can be limited by unwanted side effects such as nausea, constipation, itchiness, sedation, and respiratory depression. Additionally, their use perioperatively has been shown to result in the development of tolerance and hyperalgesia. Opioid-induced hyperalgesia (OIH) is a paradoxical increase in pain sensitivity following opioid exposure. OIH has been noted with many different opioids, but the most clinically well-documented hyperalgesic effect is with remifentanyl. Studies have attempted to reduce the development of tolerance and hyperalgesia through various agents. Their role in pain management is thought to decrease reported pain, increase the time to the patient's first request for pain medication, and lower the cumulative dose of pain medications over the first 48 hours postoperatively. Recent research by [name] have shown the mechanism for OIH in rats is due to an alteration in opioid receptor signaling and activation and hypertrophy of spinal glial cells (gliosis), and that this response can be attenuated by ultra-low dose opioid antagonists. However, there are no prospective, randomized clinical studies that have evaluated the effects ultra-low dose opioid antagonist naloxone on preventing OIH. The purpose of this study is to evaluate whether using ultra-low dose naloxone, an opioid antagonist, has the potential to block remifentanyl-induced hyperalgesia and tolerance following surgery. There are 3 study groups: (1) low dose remifentanyl infusion (LO, titrated from 0 to 0.2 mcg for an estimated average of 0.1 micrograms/kg/min), (2) high dose remifentanyl infusion combined with placebo (HI, titrated from 0.3 to 0.5 mcg for an estimated average of 0.4 micrograms/kg/min), or (3) high dose remifentanyl infusion combined with

ultra-low dose naloxone (HN, titrated from 0.3 to 0.5 mcg for an average of 0.4 micrograms/kg/min remifentanil with 0.004 micrograms/kg/min naloxone). The hypothesis of the study is that occurrence of remifentanil-induced hyperalgesia (low score in mechanical pain threshold) in the HN group will be lower than in the HI group. Adult patients (over 18 years old) undergoing similar surgeries will be selected via routine clinical care. Patients who consent to participate in the study will be administered naloxone or placebo alongside Remifentanil and data will be collected using self-reported and physiological measures.

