Attempts have been made with various agents to reduce the development of tolerance and hyperalgesia following remifentanil. Postoperative hyperalgesia and its prevention has been studied with ketamine[10, 11, 15-36], Magnesium [12, 34, 37], Gabapentin[16], Clonidine[19, 38], Lornoxicam [18], Dextromethorphan [39], Paracetamol [40, 41], Morphine [42], Dexmedetomidine [43], Adenosine [44, 45], COX inhibitors [46, 47], Amantadine [48], Nitrous oxide [49], Fentanyl [50], Pregabalin [51], Buprenorphine [52], Midazolam [53], Dexamethasone [36]. Relevant to our current hypothesis is the report that concomitant administration of ultra-low dose naloxone [13] and naltrexone [54] with remifentanil prevented OIH. However, there are no studies on reducing the adverse effects of remifentanil with ultra-low dose naloxone in human subjects. While the traditional role of opiate antagonists have been in cases of opioid overmedication, recent evidence is emerging regarding their use in pain management. Gan et al. 1997 used an ultra-low dose naloxone infusion (0.00025 mg/kg/h or 0.001 mg/kg/h) in postoperative patients receiving IV morphine via a patient-controlled analgesia (PCA) device. Good pain relief was experienced in all groups, however consumption of PCA morphine was significantly reduced in patients that received the lowest infusion of naloxone and opioid-induced side effects (nausea, vomiting, pruritus) were reduced by naloxone at both dose.

Describe the primary outcome variable(s), secondary outcome variables, and predictors and/or comparison groups as appropriate for the stated study objectives/specific aims:

The primary outcome variable of the study will be to determine the occurrence of OIH in high dose remifentanyl treatment group compared to a low dose Remifentanyl group and a high dose Remifentanyl dose with ultralow dose naloxone. OIH will be determined by assessing evoked pain thresholds. Secondary outcomes will include verbal assessment of overall pain levels via validated standard pain questionnaires and post-operative opioid consumption to determine presence of opioid analgesic tolerance. The predicted outcome is that ultralow dose naloxone will attenuate the development of remifentanyl-induced OIH. Primary outcome: Mechanical pain threshold, determined by von Frey filaments, around the incision site at 24 and 48h post-surgery. Primary hypothesis: The mechanical pain thresholds at 48h in the HN group is higher than in the HI group. Secondary

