hypotheses: 1. The mechanical pain thresholds at 48h in the LO group is higher than in the HI group. 2. The mechanical pain thresholds at 24h in both HN and LO group is higher than in the HI group. Secondary outcomes: - Opioid consumption required to control pain over the first 24 and 48h post-operatively. - Cold pressure test for pain threshold and pain tolerance - VAS pain scores measured prior to surgery and at 4, 8 and 12h after extubation and again at 24h and 48h post-operatively. - McGill short form questionnaire to be filled out prior to surgery and at 48h post-operatively - Brief Pain Inventory questionnaire to be filled out prior to surgery and at 48h post-operatively Other data collected will include a baseline history questionnaire (for demographics, age, sex, weight, income level) and the Public Health Questionnaire (PHQ-9) to measure depression as mood greatly influences pain perception. The PHQ-9 will be used to determine whether groups have been stratified appropriately.

List up to ten relevant references/articles to support the rationale for the research:

1. Bekhit, M.H., Opioid-induced hyperalgesia and tolerance. *Am J Ther*, 2010. 17(5): p. 498- 510. 2. Lin, S.L., et al., Co-administration of ultra-low dose naloxone attenuates morphine tolerance in rats via attenuation of

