kept in the research folder, which is kept in the hospital or shredded when it is not needed. If subject data is kept on a computer, the data will only be stored on hospital computers. Subject information will not be shared beyond the IRB approved research team as listed in Section 2 of this protocol narrative. Once consented, the subjects will be randomized by the study team into one of the three study groups: (1) low dose remifentanyl, (2) high dose remifentanyl combined with ultra-low dose naloxone or (3) high dose remifentanyl combined with placebo. The randomization list will be prepared before the study starts using a random number table generator and the study coordinator will obtain the information for each subject after consent. Personnel directly involved in subject care will be blinded as to naloxone or placebo administration. The pain assessors (second blinded group) will be blinded. Surgical procedures will not be altered and subjects will still receive standard subject care. Following consent, a packet of questionnaires (includes baseline questionnaire, Public Health Questionnaire (PHQ-9), VAS, McGill Short Form, Brief Pain Inventory) will be provided to subjects by study staff. All subjects will be required to complete a baseline questionnaire to obtain subject demographics prior to surgery. Opioid-induced hyperalgesia OIH will be measured by determining experimentally induced pain thresholds and clinically meaningful outcomes of pain via validated pain questionnaires and post-operative opioid consumption. These outcomes have previously been used and validated to assess remifentanyl-induced hyperalgesia; pain thresholds to cold and static mechanical stimulation are the most common pain modalities altered by remifentanyl infusion. Experimentally induced pain will be performed in pre-op by quantitative sensory testing via von Frey filaments applied in ascending order to the dorsal surface of the subject's non-dominant hand and 5cm from the incision site. Subjects will be instructed to indicate when stimulus produces a painful sensation as well as when the stimulus becomes unpleasant. In addition to determination of mechanical pain thresholds, cold pain threshold and tolerance will be determined. Subjects will be instructed to immerse their hand in a bucket of ice water and indicate when they first experience a painful sensation (threshold) and to remove their hand from the ice water when they can no

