longer tolerate the pain (tolerance). The time for pain tolerance and threshold will be recorded. Validated pain questionnaires will be administered to subjects prior to surgery and 48h after cessation of remifentanyl infusion. These questionnaires will include the McGill Short Form pain questionnaire and the Brief Pain Inventory (short form). The McGill questionnaire provides an assessment of pain quality and descriptors, whereas the Brief Pain Inventory assesses both pain intensity and pain unpleasantness (the emotional component of pain is considered to be a better metric of subject satisfaction and quality of life). A research assistant blind to treatment will administer both experimentally induced pain assessments and pain questionnaires before surgery and after the surgery. As part of the study, subject demographics (age, gender, surgery type) and hemodynamics (heart rate, blood pressure, etc) that are obtained as standard operating room procedure will be accessed. Measures will be taken to protect subject privacy by only allowing IRB approved research personnel to access records as needed. The table below indicates the timing and outcome measures that will be determined.

	Pre-op Consult	Post-surgery	4h	8h	12h	24h	48h	PHQ-9	VAS	McGill Pain Questionnaire	UCI IRB Approved: 08-26-2021   MOD# 29836
Baseline History	x										
Brief Pain Inventory		x									
Von Frey Testing		x	x	x							
Cold Pressor Test		x	x	x							
Opioid Consumption		x	x	x	x	x					

Statistical Considerations 1. Statistical Analysis Plan: Describe the statistical method(s) for the stated specific aims and hypotheses described in Section 1. Note: Required for scientific review. 2. Explain how the overall target sample size was determined (Provide power / sample size justification for the study). If a statistical analysis plan is not appropriate for your study design, please describe a plan for assessing your study results. Statistical Analysis Plan For the primary outcome, the 2-sample t-test will be applied to compare the difference in mechanical pain thresholds at 24 and 48h between HN and HI group, and between LO and HI group. For the secondary outcomes, the continuous variables will also be analyzed using 2-sample t-test to identify the difference between HN and HI group, and between LO and HI group. The mean level and corresponding 95% confidence interval (CI) will be obtained for each study

group. The categorical outcomes will be analyzed 1 Pre-op Consult  

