### **Statistical Considerations**

Is a statistical analysis plan appropriate for this qualitative study design?

Yes

Describe the statistical methods for the stated specific aims and hypotheses. Your analysis plans should match the stated study specific aims and hypotheses:

For the primary outcome, the 2-sample t-test will be applied to compare the difference in mechanical pain thresholds at 24 and 48h between HN and HI group, and between LO and HI group. For the secondary outcomes, the continuous variables will also be analyzed using 2-sample t-test to identify the difference between HN and HI group, and between LO and HI group. The mean level and corresponding 95% confidence interval (CI) will be

obtained for each study group. The categorical outcomes will be analyzed using the chi-square test and the odds ratio (compare to HI group) and corresponding 95% CI will also be obtained.

Describe the statistical method(s) that will be used to analyze the primary outcome(s) or endpoints:

see above

If appropriate describe secondary or post hoc analyses of primary outcome(s) or other exploratory analysis and if necessary, provide a breakdown of the methods used per outcome or endpoint:

Secondary outcomes: - Opioid consumption required to control pain over the first 24 and 48h post-operatively. - Cold pressure test for pain threshold and pain tolerance - VAS pain scores measured prior to surgery and at 4, 8 and 12h after extubation and again at 24h and 48h post-operatively. - McGill short form questionnaire to be filled out prior to surgery and at 48h post-operatively - Brief Pain Inventory questionnaire to be filled out prior to surgery and at 48h post-operatively

**Sample Size Determination:** Explain how the overall target sample size was determined (e.g., power analysis; precision estimation), providing justification of the effect size for the primary outcome based on preliminary data, current knowledge/literature and/or cost consideration; if appropriate, provide sample size justification for secondary outcomes. Power analysis should (at least) match the primary outcome/endpoint:

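### Any posterior spinal fusion is eligible, but surgical extent is used in neither randomisation nor analysis, so precision may be lost

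*Combined protocol and SAP*

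**What the plan says.** - **Eligibility.** Under Eligibility Factors (Inclusion/Exclusion Criteria), the surgical criterion is "4. Surgery: Posterior spinal fusions". No exclusion refers to number of levels, spinal region or revision surgery. The description of subject identification under Waiver of HIPAA Authorization adds no limit. The lay summary in the Project Screener says that adults "undergoing similar surgeries will be selected via routine clinical care", but no criterion defines similar.
- **Randomisation.** Study Design: "The randomization list will be prepared before the study starts using a random number table generator". Neither strata nor blocks are described. The one reference to stratification, in Background & Purpose of the Research, concerns depression: "The PHQ-9 will be used to determine whether groups have been stratified appropriately".
- **Data.** Study Design lists "subject demographics (age, gender, surgery type" among the variables taken from the record. Number of levels, incision length and infusion time are not named, and surgery type has no role in the analysis.
- **Primary outcome.** "Mechanical pain threshold, determined by von Frey filaments, around the incision site at 24 and 48h post-surgery". Study Design places the test 5 cm from the incision, and also on the hand, and schedules a pre-operative measurement.
- **Analysis.** Statistical Considerations: "the 2-sample t-test will be applied to compare the difference in mechanical pain thresholds at 24 and 48h between HN and HI group", and likewise for LO against HI. Continuous secondary outcomes are handled the same way. No covariate is mentioned.

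**The concern.** Posterior spinal fusion can be a short or a long construct, and a first or a repeat operation. The primary outcome is sensitivity next to the wound, and the secondary outcomes include pain scores and opioid use. It is plausible that these depend on how much surgery was done. Planned extent is knowable before randomisation, so it can be used safely in both allocation and analysis, and the plan uses it in neither.

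What is at stake is efficiency. A prognostic factor left out of the model widens the confidence interval for HN against HI, and a chance difference in case mix between two arms of about 32 moves the unadjusted estimate. In a small single-centre trial aimed at a fairly large effect (0.71 SD), precision available for one extra data field is worth having.

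**Working it through.** **Inputs from the documents** (Sample Size Determination): two-sided alpha 0.05, two-sample t-test, 105 recruited (35 per group), 8% attrition, 96 analysed; 80% power at 0.71 SD and 90% at 0.82 SD.

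**Inputs not in the documents (assumed):** R², the share of within-arm outcome variance explained by planned extent, taken as 5, 10, 20 and 30%; and the prevalence of a two-category extent variable, taken as 50% or 30%.

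**1. Reproduce the plan's figures.** 35 × 0.92 = 32.2, so 32 per group and 96 in all. With the noncentral t at 32 per group, the detectable effect is 0.711 SD at 80% power and 0.823 SD at 90%. Power at 0.71 is 79.8% and at 0.82 is 89.8%. The stated figures hold.

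**2. Gain from adjusting for extent.** Adjustment reduces the residual SD by the factor √(1 − R²), so the effective standardised effect is 0.71/√(1 − R²). Degrees of freedom are 64 − 3 = 61. The unadjusted sample that would be worth the same is about 32/(1 − R²) per arm.

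| Assumed R² | Effective effect | Power, 32 per arm | Detectable at 80% (0.711 × √(1 − R²)) | Equivalent unadjusted n per arm |
|---|---|---|---|---|
| 0 | 0.710 | 79.8% | 0.711 | 32 |
| 5% | 0.728 | 81.8% | 0.693 | 33.7, so 34 |
| 10% | 0.748 | 83.8% | 0.675 | 35.6, so 36 |
| 20% | 0.794 | 87.8% | 0.636 | 40 |
| 30% | 0.849 | 91.6% | 0.595 | 45.7, so 46 |

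**3. If 0.71 was meant for surgically homogeneous patients.** Extent would then add to the SD, and the effect in total-SD units would be 0.71 × √(1 − R²) = 0.692, 0.674, 0.635 or 0.594. Unadjusted power would be 77.8, 75.6, 70.6 or 64.8%. The plan gives neither an SD nor a raw difference, so this cannot be settled either way.

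**4. Chance imbalance.** With 32 per arm and a feature present in half of patients, the SD of the difference in proportions is √(2 × 0.5 × 0.5/32) = 0.125. From exact binomials, HN and HI differ by at least 15 percentage points in 26% of trials and by at least 20 points in 10%. At 30% prevalence these are 22% and 8%.

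To see what that does to the estimate: a half-prevalence feature explaining R² of the variance separates its two categories by 2√R² SD. A 15-point imbalance therefore shifts the HN − HI difference by 0.15 × 2√R², which is 0.07 SD at 5% and 0.16 SD at 30%. The standard error of the comparison is √(2/32) = 0.25 SD.

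**5. The closed trial.** Eight participants over three arms is 8/3, or about 3 per arm. At 3 per arm, the effect detectable with 80% power is 3.07 SD. A two-arm model with intercept, treatment, extent and baseline would leave 6 − 4 = 2 degrees of freedom.

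**The case against.** An unadjusted t-test in a randomised trial is valid, and chance imbalance is already allowed for in its error rate and confidence interval. The imbalance in step 4 stays below one standard error even at the top of the assumed range. At the low end of that range, adjustment is worth only 2 to 4 points of power, and nothing in the documents favours the high end. The threshold is tested at a fixed 5 cm from the incision, so an effect of wound size on it is plausible but not shown. All of this stands, and it keeps the point at the level of a cheap improvement.

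It also stands that surgery type is not extent. Every patient has a posterior fusion, so the recorded field may say little about levels. Nor do the documents show that the surgical schedule lists planned levels. Finally, the pre-operative threshold is another unused covariate, and how much extent adds once it is in the model is unknown.

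A reader might infer more than the text supports:

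- **That differences in wound and infusion length are large.** No section gives levels, incision length, operating time or infusion time, or links any of them to the threshold.
- **That the comparison is biased or the power statement false.** Randomisation balances extent in expectation. The 0.71 is in SD units, and that SD may already include surgical variation.
- **That total remifentanil exposure overlaps between LO and HI because the arms are defined by rate.** At the summary's estimated averages of 0.1 and 0.4 micrograms/kg/min, equal totals need a 0.4/0.1 = fourfold difference in infusion time, and no times are given. HN and HI share one rate range, so the argument does not reach the primary comparison.
- **That the lay summary's reference to similar surgeries is a broken promise.** Restriction to one class of procedure is a fair reading of it.

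**Conclusion.** The concern holds as a possible loss of precision. Eligibility is open on surgical extent, the list is unstratified, and the analysis is unadjusted, so any effect of extent on the outcomes is left as noise. On assumed R² of 5 to 30%, using planned extent would add about 2 to 12 points of power at 0.71 SD with 32 per arm, equivalent to 34 to 46 analysed per arm instead of 32. If extent explains almost nothing, the gain is almost nothing.

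The range rests on two assumptions: the R² values themselves, and planned extent being the only covariate. With the pre-operative value also in the model, the R² should be read as what extent explains beyond it. The planned test remains valid and the stated power reproduces.

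**What to change.** For the design as written, or any re-run:

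- Record planned surgical extent before randomisation, for example 1–2 versus 3 or more planned levels. Name it as its own data item, since surgery type does not supply it.
- Stratify the randomisation list by that category, with blocks within each stratum. A simple random list within each stratum would not balance the arms.
- Replace the t-test with a linear model for the primary and continuous secondary outcomes, containing treatment, planned extent and, where measured, the pre-operative value of the outcome. For the primary outcome that is the threshold at the same site, which Study Design already collects. Keep the planned HN–HI and LO–HI contrasts.
- Do not adjust for achieved infusion time. It arises after randomisation and is part of the exposure. Report it descriptively.

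Cost: one recorded field, one stratification factor, and one or two degrees of freedom. No extra patients or procedures.

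For the closed trial, the closure form reports 8 of 105 enrolled, data collection complete and analysis not yet done. Stratification is no longer possible and adjustment is not workable. List surgical extent, taken from existing surgical records, beside each participant's result when the results are reported.
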